APPENDIX III - Guidelines for SRS/SBRT dosing and fractionation

Guidelines for SRS (see also section 6.2)

CNS

Treatment will be performed with single fraction SRS/SBRT. Patient will be positioned in supine position with appropriate fixation device, frameless SRS/SBRT can be performed if set-up uncertainty is minimal. SRS/SBRT doses are dependent on lesion size as follows:

Lesion Diameter (cm)	SRS/SBRT dose (Gy)
< 2	24/ 1 fx
2-3	18/ 1 fx
> 3	15 / 1 fx
> 4	30 / 3 fx

For larger lesions, fractionated SRS/SBRT may be used (3 fractions of 10 Gray per fraction) instead of a single fraction of 15 Gy.

LUNG

SBRT to lung lesions will consist of 3-5 treatments depending on location of tumor. Patient will be positioned in supine position with gated treatments or tumor tracking with fiducial markers. For central tumors (defined as within 2 cm of carina, right and left main bronchi, right and left upper lobe bronchi, intermedius bronchus, right middle lobe bronchus, lingular bronchus, and left lower lobe bronchus) SRS dose will be 48 Gy in 4 fractions. For non-central lesions, SBRT dose will be 60 Gy in 3 fractions.

Dose constraints for 48 Gy in 4 fractions:

Organ	Volume	Volume Max	Max Point Dose
Spinal Cord	<0.25 cc	22.5 Gy (4.5 Gy/fx)	30 Gy (6 Gy/fx)
Skin	<10 cc	30 Gy (6 Gy/fx)	32 Gy (6.4 Gy/fx)
Lung (both right and left lung volumes)	1500 cc	12.5 Gy (2.5 Gy/fx)	
Skin	< 10 cc	33.2 Gy (8.3 Gy/fx)	36 Gy (9 Gy/fx)
Chest wall	Any point	32 Gy (8 Gy/fx)	40 Gy (10 Gy/fx)

Dose constraints for 60 Gy in 3 fractions:

Organ	Volume	Max Point Dose
Spinal Cord	Any point	18 Gy (6 Gy per fx)
Esophagus	Any point	27 Gy (9 Gy per fx)
Heart/Pericardium	Any point	30 Gy (10 Gy per fx)
Bronchus	Any point	30 Gy (10 Gy per fx)
Skin	Any point	24 Gy (8 Gy per fx)
Chest wall	Any point	24 Gy (8 Gy per fx)

ADDRENAL

SBRT dose will be 50 Gy in 5 fractions. Patient will be positioned in supine position with gated treatments or tumor tracking with fiducial markers.

Dose constraints

Normal Tissue Constraints	
Organ	Maximum Dose in 5 Fractions
Contralateral Kidney (2/3 volume)	5 Gy
35% of Total (left & right) Kidney Volume	25 Gy
Spinal Cord	20 Gy
Stomach	35 Gy

BONE

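### In Appendix III, the lung table for 48 Gy in 4 fractions mixes 4- and 5-fraction limits, and its spinal-cord row is on the 5-fraction basis

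*Combined protocol and SAP*

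**What the plan says.** The LUNG part of Appendix III opens with "SBRT to lung lesions will consist of 3-5 treatments depending on location of tumor". It then names two schedules. For central tumors, "SRS dose will be 48 Gy in 4 fractions"; for other lesions, 60 Gy is given in 3. No 5-fraction lung dose is named.

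Two constraint tables follow. The first is headed "Dose constraints for 48 Gy in 4 fractions". Its Spinal Cord row gives "22.5 Gy (4.5 Gy/fx" for <0.25 cc, and a point maximum of 30 Gy at 6 Gy per fraction. The Lung row gives "12.5 Gy (2.5 Gy/fx". Skin for <10 cc appears in two rows: first with 30 and 32 Gy, later with "33.2 Gy (8.3 Gy/fx" and 36 Gy. The second table, for 60 Gy in 3 fractions, limits the cord to "18 Gy (6 Gy per fx".

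Elsewhere in Appendix III, the adrenal table gives 20 Gy for the cord under "Maximum Dose in 5 Fractions". The liver prose gives a cord point maximum of 18 Gy in 3 fractions and 20 Gy in 5. The liver table gives 18 Gy in its 3-fraction column and 20 Gy in its 4-fraction column. The liver section offers 3 or 4 fractions only.

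Section 6.2.6 leaves the exact dose and fractionation to the treating physician and encourages use of Appendix III.

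**The concern.** A planner treating a central lung lesion reads this table for 4 fractions. In the cord row, the total and the per-fraction dose cannot both describe 4 fractions: 6 Gy per fraction allows 24 Gy, while 30 Gy allows 7.5 Gy per fraction. The cell does not say which one governs. Someone who reads only the total takes the less protective figure.

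At stake is a spinal-cord limit that planners are encouraged to follow, in a trial whose primary objective is the safe delivery of SBRT to multiple sites. The duplicated Skin row points the same way: rows from two schedules appear to have been combined under one title.

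**Working it through.** **Inputs.** All come from Appendix III: the nine dose cells of the lung 4-fraction table, the lung 3-fraction table, the adrenal table, and the liver prose and table.

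**Step 1. Number of fractions implied by each cell.** Implied fractions = printed total / printed dose per fraction. The 4-fraction total is 4 × the printed dose per fraction.

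| Cell | Total (Gy) | Gy per fraction | Implied fractions | 4 × per-fraction dose (Gy) | Ratio |
|---|---|---|---|---|---|
| Cord, <0.25 cc | 22.5 | 4.5 | 5 | 18 | 1.25 |
| Cord, point | 30 | 6 | 5 | 24 | 1.25 |
| First Skin row, <10 cc | 30 | 6 | 5 | 24 | 1.25 |
| First Skin row, point | 32 | 6.4 | 5 | 25.6 | 1.25 |
| Lung, 1500 cc | 12.5 | 2.5 | 5 | 10 | 1.25 |
| Second Skin row, <10 cc | 33.2 | 8.3 | 4 | 33.2 | 1.00 |
| Second Skin row, point | 36 | 9 | 4 | 36 | 1.00 |
| Chest wall, volume column | 32 | 8 | 4 | 32 | 1.00 |
| Chest wall, point | 40 | 10 | 4 | 40 | 1.00 |

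Five cells imply 5 fractions and four imply 4. Only the four match the table's title.

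**Step 2. The neighbouring table as a control.** In the table for 60 Gy in 3 fractions, every row implies 3: cord 18/6, esophagus 27/9, heart 30/10, bronchus 30/10, skin 24/8, chest wall 24/8. So dividing total by per-fraction dose is the right way to read these cells.

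**Step 3. The two readings of the cord row at 4 fractions.**
- Per-fraction doses govern: 4 × 4.5 = 18 Gy and 4 × 6 = 24 Gy.
- Totals govern: 22.5 / 4 = 5.625 and 30 / 4 = 7.5 Gy per fraction, against 4.5 and 6 printed.

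A plan that meets both printed numbers is held to 18 and 24 Gy.

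**Step 4. The liver labels.** Figures in Gy:

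| Structure | Prose, 5 fractions | Table, 4-fraction column |
|---|---|---|
| Liver (700 cm³) | 25 | 25 |
| Right kidney (2/3) | 25 | 25 |
| Total kidney (35%) | 25 | 25 |
| Spinal cord | 20 | 20 |
| Stomach | 35 | 35 |

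All five match, although the fraction labels differ and the section offers no 5-fraction schedule.

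**The case against.** **Status of the appendix.** Appendix III is guidance, and section 6.2.6 gives the physician discretion over dose and fractionation. That limits the weight of the point. But section 6.2.6 does not expressly extend that discretion to organ limits, and discretion does not settle what a self-contradictory cell means.

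**A text-extraction error.** This is possible in principle but unlikely. Five pairs of numbers divide exactly to 5, and the extra Skin row has its own complete set of values.

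**The 3-5 treatments in the lung text.** A 5-fraction lung course is within that range. The title of the table is still 4 fractions, and no 5-fraction lung dose is named for these rows to serve.

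**A stronger reading.** A reader might infer that the lung cord maximum is simply too high, because 30 Gy is 10 Gy (50%) above the 20 Gy printed in the adrenal and liver sections. The documents do not support that conclusion:
- Nothing requires cord limits to match across sites.
- The lung table has a volume tier as well as a point maximum.
- The adrenal table does not say that its maximum is a point dose.
- The only 4-fraction comparator is the liver column that Step 4 shows to be doubtful.
- A plan that also respects 6 Gy per fraction reaches 24 Gy over 4 fractions, a gap of 4 Gy (20%).

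What remains is a fair question. The liver prose limits any point of the cord to 20 Gy in 5 fractions, the lung row divides out to 30 Gy in 5, and the two sites agree at 18 Gy in 3 fractions. No reason is given for the divergence. The example in section 6.2.6 treats lung, liver and adrenal lesions in one patient, so one planner could meet all of these limits together.

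**Conclusion.** The point holds as an internal inconsistency in a safety guideline, and it should be fixed. In the lung 4-fraction table, five of nine cells are on a 5-fraction basis, with totals 25% above what their own per-fraction doses allow over 4 fractions. Both cord limits are among them. Skin <10 cc also carries two different pairs of limits. The liver section has a related labelling fault in all five rows.

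This rests on one assumption: that the bracketed number in each cell is the per-fraction dose for the same limit. The 3-fraction table bears that out.

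The arithmetic is certain; the intended values are not. The documents do not show whether the totals or the per-fraction doses are right, nor whether the lung cord maximum is meant to differ from the 20 Gy printed elsewhere. A reader might also infer harm to patients or a distorted toxicity result. The documents do not support either: they do not say how many central lung lesions lie near the cord, or how plans were made. No effect on the sample size or analysis is claimed.

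**What to change.** Make one amendment to Appendix III, with values set by the sponsor's radiation oncologists and physicists:

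1. Put every row of the lung 4-fraction table on a 4-fraction basis, with total and per-fraction dose agreeing.
2. Delete the duplicate 5-fraction Skin row. This leaves 33.2 and 36 Gy, which are higher totals than the 30 and 32 Gy removed, so they should be confirmed as intended.
3. Correct the liver section so that prose and table give limits for the same schedules, namely the 3 and 4 fractions it offers.
4. As a query only, ask the sponsor whether the lung cord point maximum is meant to exceed the 20 Gy in the adrenal table (5 fractions), the liver prose (any point, 5 fractions) and the liver table (4 fractions). If so, print the reason.

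Until the sponsor confirms the values, planners using 4 fractions should satisfy both printed caps: cord at most 18 Gy to <0.25 cc and 24 Gy at any point. This is a precaution and does not imply that these are the intended limits.

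The cost is an amendment to one appendix. Some central lung plans near the cord may need tighter cord sparing; the documents do not allow an estimate of how many.

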Appendix IV - Sample of QOL form (FACT-G)

FACT-G (Version 4)

Below is a list of statements that other people with your illness have said are important. Please circle or mark one number per line to indicate your response as it applies to the past 7 days.

PHYSICAL WELL-BEING		Not at all	A little bit	Some-what	Quite a bit	Very much
GP1	I have a lack of energy	0	1	2	3	4
GP2	I have nausea	0	1	2	3	4
GP3	Because of my physical condition, I have trouble meeting the needs of my family	0	1	2	3	4
GP4	I have pain	0	1	2	3	4
GP5	I am bothered by side effects of treatment	0	1	2	3	4
GP6	I feel ill	0	1	2	3	4
GP7	I am forced to spend time in bed	0	1	2	3	4
SOCIAL/FAMILY WELL-BEING		Not at all	A little bit	Some-what	Quite a bit	Very much
GS1	I feel close to my friends	0	1	2	3	4
GS2	I get emotional support from my family	0	1	2	3	4
GS3	I get support from my friends	0	1	2	3	4
GS4	My family has accepted my illness	0	1	2	3	4
GS5	I am satisfied with family communication about my illness	0	1	2	3	4
GS6	I feel close to my partner (or the person who is my main support)	0	1	2	3	4
Q1	Regardless of your current level of sexual activity, please answer the following question. If you prefer not to answer it, please mark this box  and go to the next section.					
GS7	I am satisfied with my sex life	0	1	2	3	4

FACT-G (Version 4)

Please circle or mark one number per line to indicate your response as it applies to the past 7 days.

EMOTIONAL WELL-BEING		Not at all	A little bit	Some- what	Quite a bit	Very much
GE1	I feel sad.....	0	1	2	3	4
GE2	I am satisfied with how I am coping with my illness.....	0	1	2	3	4
GE3	I am losing hope in the fight against my illness.....	0	1	2	3	4
GE4	I feel nervous.....	0	1	2	3	4
GES	I worry about dying.....	0	1	2	3	4
GE6	I worry that my condition will get worse.....	0	1	2	3	4

FUNCTIONAL WELL-BEING		Not at all	A little bit	Some- what	Quite a bit	Very much
GF1	I am able to work (include work at home)	0	1	2	3	4
GF2	My work (include work at home) is fulfilling.....	0	1	2	3	4
GF3	I am able to enjoy life.....	0	1	2	3	4
GF4	I have accepted my illness.....	0	1	2	3	4
GF5	I am sleeping well	0	1	2	3	4
GF6	I am enjoying the things I usually do for fun.....	0	1	2	3	4
GF7	I am content with the quality of my life right now.....	0	1	2	3	4
